The Whirl-Pak bags containing the samples will be kept on ice in an isolation box and processed within 4 hours of sampling (45). Membrane filtration will be used to detect colony-forming units (CFUs) of *E. Coli* and total coliforms. In a field laboratory, the content of the bags will be passed through a 47-mm-diameter 0.45 µm cellulose filter. The filter paper will then be placed on growth media and incubated at 35°C ± 0.5°C for a duration of 24 hours for *E. Coli* and total coliforms (45). We plan to filter 100 mL per bag to detect CFUs of *E. Coli* and total coliforms. The exact amount of mL will be established during piloting as the volume used is dependent on the degree of bacterial contamination on the hands. Compact dry plates will be used for the detection of *E. coli* and total coliforms.

The lower detection limit of CFUs will be calculated by dividing 1 CFU/plate by the filtrate volume and then multiplying it with the total Whirl-Pak volume of 350 mL. The upper detection limit will be calculated by dividing 500 CFUs/plate by the filtrate volume and then multiplying it with the Whirl-Pak volume. For the statistical analysis, the CFUs per hand will be normalized and \log_{10} transformed (45).

Module 4: Diary approach for pre-defined health outcomes: Longitudinal data on hygiene-related health outcomes of patients and disease-related absences of HCWs will be collected during

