4.2 Secondary endpoints

The most important secondary endpoints in the survey are:

- A) Self reported handwashing practice to answer for each critical moment on a Likert scale ranging from almost never to almost always.
- B) The log-transformed number of total coliforms and E.coli CFUs per hand before handwashing.
- C) Hygiene-related health outcomes which are summarized in table 3. The sum of each outcome variable separately per facility will be used as a measure for statistical analysis. The health outcomes will be reassessed with local experts of the respective countries to assure feasibility before the start of the intervention.

Table 3: Hygiene-related health outcome variables for Module 4.

Outcome variable	Details
Absenteeism of health care worker	
 • Record of the event • Number of days absent • Reason for absence
Maternal mortality	
 • Record of the event • If known, reason of passing
Neonatal mortality	
 • Record of the event • If known, reason of passing
Neonatal sepsis(49)	
 • Record of the event • Number of days treated • Outcome (healthy, unknown, death)
Umbilical cord infection	
 • Record of the event • Number of days treated • Type of infection • Outcome (healthy, unknown, death)
Wound infection after stitching of surgical procedures	
 • Record of the event • Number of days treated • Outcome

Covariates were assessed with a directed acyclic graph (DAG) with RANAS variables as exposure variables and good handwashing practice as outcome variable (Appendix). Covariates for estimating the total effect of RANAS on good handwashing practice are age, education, sex, socio-economic status, previous training in hygiene, handwashing practices, position in the health care facility, and the water infrastructure of the health care facilities.

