7.3 Confidentiality and coding

Project data will be handled with uttermost discretion and is only accessible to authorized personnel who require the data to fulfil their duties within the scope of the research project. On the CRFs and other project specific documents, participants are only identified by a unique participant number (ID). The CRFs contain the ID assigned to the participant by the field staff. The name of the participant will be kept in a separate confidential enrolment log that matches identifying codes with the participants' names and residencies during the study. This will only be accessible by the local study coordinator and the people conducting the survey. The document will be stored in the locked cabinet on site and destroyed after the end survey in order to completely anonymize participants.

Biological material (the hand rinse samples) in this project is not identified by participant name but by a unique participant ID. Biological material is appropriately stored in a restricted area only accessible to authorized personnel for a maximum of 48h to be analysed.

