7.4 Retention and destruction of study data and biological material

The study data, including video and audio material, will be stored on the Swiss TPH server and stays there for a time span of 10 years after publication of the research project. The informed consent forms on paper will be kept in a folder, locked at the study site for 10 years. After 10 years electronic data will be deleted and the papers will be shredded and disposed of. The participant identification list and the paper informed consent forms after scanning will be immediately destroyed after the end survey to guarantee anonymity after the survey.

Biological material, more specifically the compact dry plates containing hand-rinse samples will be destroyed and disposed after a maximum of 48 hours. The plates have to be disinfected before being disposed of in waste bins. This can either happen by a) putting them into a covered bucket containing 1% bleach solution over night. The next morning, the bleach solution will be emptied into the waste water and the plates can be disposed in a plastic bag in any normal waste bin. Or b) the closed plates are placed in a pot of boiling water for a minimum of 10 minutes. After the water cools, it can be emptied into the waste water and the plates can be disposed in a waste bin.

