8.4 Storage of biological material and related health data

Water samples and hand-rinse samples will be stored in a refrigerator for a maximum of 48 hours until analysis. If unfiltered water is left from health care facilities, it will be discarded in the drain after resting for 30 minutes with 10mg/L of chlorine. For the analysis, CFUs will be counted and the plates will be photographed. The pictures will be stored in the same way as other health-related data. After counting the CFUs and recording the compact dry plates with pictures, they have to be destroyed immediately to prevent any further growth of potentially harmful bacteria (see chapter 7.4 Retention and destruction of study data and biological material).

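### Module 3 requires hand-rinse samples to be processed within 4 hours, but section 8.4 (and possibly 7.3) allows them to be held for up to 48 hours, and holding time is not planned to be recorded or analysed

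*Combined protocol and SAP*

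**What the plan says.** Four places in the protocol bear on how long hand-rinse material may be kept.

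- **Section 4, Module 3.** Bags are to be "kept on ice in an isolation box and processed within 4 hours of sampling". The contents are then filtered in a field laboratory and incubated at 35 °C "for a duration of 24 hours". The protocol attaches the 4-hour limit to the published hand-rinse method that it follows.
- **Section 8.4.** "Water samples and hand-rinse samples will be stored in a refrigerator for a maximum of 48 hours until analysis".
- **Section 7.3.** This section identifies its subject: "Biological material (the hand rinse samples) in this project is not identified by participant name". It then says that the material is stored in a restricted area, "only accessible to authorized personnel for a maximum of 48h to be analysed".
- **Section 7.4.** Here 48 hours belongs to a later step: "the compact dry plates containing hand-rinse samples will be destroyed and disposed after a maximum of 48 hours".

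The measurement at stake is secondary endpoint B in section 4.2: "The log-transformed number of total coliforms and E.coli CFUs per hand before handwashing". Section 4.3 provides for checks by data-collector ID, duplicate samples, second counts and blinded counting. It does not mention time from sampling to filtration.

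**The concern.** Two operating rules for the same bags give different outer limits and different storage conditions (ice box, refrigerator). Numbers of viable bacteria in stored rinse water may change before filtration, and the later quality checks cannot undo that. Blinded counting protects the reading of the plate, not what happened to the sample beforehand. If holding time varies between facilities, it adds noise to the CFU comparison. If it also happens to differ by arm, it adds bias. The plan does not say that either time will be recorded, so the analysis could neither detect nor describe the problem afterwards.

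**Working it through.** **1. What each limit covers**

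| Section | Object | Condition | Limit | Step |
|---|---|---|---|---|
| 4, Module 3 | hand-rinse bags | on ice | 4 h | sampling to processing |
| 8.4 | water and hand-rinse samples | refrigerator | 48 h | until analysis |
| 7.3 | hand-rinse samples | restricted area | 48 h | to be analysed |
| 7.4 | compact dry plates | not stated | 48 h | until destruction |

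**2. Could 48 hours mean the whole path to the count?** Processing by 4 h plus 24 h of incubation is 4 + 24 = 28 h, which fits inside 48 h. Section 7.3 can be read that way. Section 8.4 cannot easily be, for three reasons. It puts samples in a refrigerator, whereas plates are incubated at 35 °C. It goes on to deal with leftover unfiltered water, and only then with counted plates. And 7.4 already gives plates a 48-hour limit of their own. So 8.4 conflicts with Module 3, and 7.3 is ambiguous.

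**3. Size of the discrepancy.** Ratio: 48/4 = 12. Difference: 48 − 4 = 44 h.

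**4. Effect on the counts.** The plan states no CFU effect, standard deviation or storage-change rate, so there is no figure to reproduce. What follows is a sensitivity range on assumed values.

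Shift in one sample held 48 h rather than 4 h = k × 44/24, with k an assumed change in log10 CFU per day:

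| k (log10/day) | 0 | 0.05 | 0.1 | 0.25 | 0.5 | 1.0 |
|---|---|---|---|---|---|---|
| Shift (log10) | 0 | 0.09 | 0.18 | 0.46 | 0.92 | 1.83 |

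For scale, with the planned 100 mL filtered, the detection limits are 1/100 × 350 = 3.5 and 500/100 × 350 = 1,750 CFU per hand. They are log10(500) = 2.70 apart.

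**5. Comparison with a detectable difference.** For 80% power at two-sided 5%, the detectable difference is (1.960 + 0.842) × SD × √(2 × DE/(6K)), where DE = 1 + 5 × ICC. This takes 6 workers per facility and K facilities per arm. The assumed ranges are SD 0.5 to 1.0 and ICC 0.05 to 0.15.

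- K = 12 (24 facilities in all, section 6.2), SD 0.5, ICC 0.05: 2.802 × 0.5 × √(2 × 1.25/72) = 0.26 log10.
- K = 12, SD 1.0, ICC 0.15: 2.802 × 1.0 × √(2 × 1.75/72) = 0.62 log10.
- K = 24 (48 facilities in all, Synopsis), same two settings: 0.18 and 0.44 log10.

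With K = 12, a 44-hour gap would match the detectable difference at k = 0.26/(44/24) = 0.14 to 0.62/(44/24) = 0.34 log10 per day. That requires every sample in one arm to wait 48 h and every sample in the other 4 h. For a mean gap of 4 h between arms, k = 0.25 to 1.0 gives 4/24 × k = 0.04 to 0.17 log10.

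**The case against.** The strongest reply is that every figure is an upper limit. A team that processes each bag within 4 hours meets all the sections, so a reader who infers that they cannot all be followed goes too far. That stands. The defect is that 8.4 permits what Module 3 forbids.

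The second reply concerns bias. Facilities are allocated by stratified randomisation, CFU counters are blinded, and nothing in the documents gives travel times or suggests that holding time depends on arm. A shift common to both arms largely cancels on the log scale. This mostly stands: the likelier harm is noise or a common shift. But randomisation balances distance to the laboratory only on average, the number of facilities is small, and data collectors are not blinded.

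Third, 7.3 is weaker evidence than 8.4, since its 48 hours may run to the count. That also stands.

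A reader might further infer that longer storage could change counts by as much as the effect the trial seeks. The documents do not support this. Their only effect size, 30% versus 45%, concerns observed handwashing.

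**Conclusion.** The inconsistency is real and should be corrected. Section 8.4 states an operating rule that allows a hold 12 times as long as the plan's own method for a listed secondary endpoint, and 7.3 can be read as agreeing with it. The consequence is uncontrolled variation in endpoint B, with bias only if holding time differs by arm.

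The size cannot be settled from the documents. Under the assumed rates, the change in a sample held 44 hours longer runs from nothing to 1.83 log10. Those are worst cases for single samples and not differences between arms. Whether they matter depends wholly on assumed values for the storage rate, the SD and the ICC. The primary endpoint and its stated power are not touched.

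**What to change.** 1. State one sampling-to-filtration limit, with one storage condition, for hand-rinse samples in sections 4 (Module 3), 7.3 and 8.4. The method that Module 3 follows uses 4 hours.
2. Keep 48 hours for plates (7.4). If 48 hours was meant for water samples, say so separately in 8.4.
3. Record sampling time and filtration time on the electronic form for hand-rinse samples already listed in section 7.1. The audit trail in section 7.5 logs actions on the database, which is not the same thing.
4. Before any comparison by arm, fix a rule blind to arm that flags samples over the limit. Report the number flagged by arm, country and round, and add a sensitivity analysis that leaves them out. Because section 6.4 rules out imputation, it is better to flag late samples and keep them in the main analysis than to exclude them outright.

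The cost is wording in three sections, the recording of times on a form that already exists, and one additional analysis. The downside is that some samples from distant facilities will be flagged.

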4.1 Primary endpoint

The primary endpoint is the number of times a participant performs good handwashing practice with soap at critical moments assessed by structured handwashing observations over half an hour to an hour per HCW. The number of critical moments serves as denominator. Critical moments are defined by the WHO as:

- i) Before touching a patient
- ii) Before clean/aseptic procedures
- iii) After risk/exposure to body fluids
- iv) After touching a patient
- v) After touching a patient's surroundings

4.2 Secondary endpoints

The most important secondary endpoints in the survey are:

- A) Self reported handwashing practice to answer for each critical moment on a Likert scale ranging from almost never to almost always.
- B) The log-transformed number of total coliforms and E.coli CFUs per hand before handwashing.
- C) Hygiene-related health outcomes which are summarized in table 3. The sum of each outcome variable separately per facility will be used as a measure for statistical analysis. The health outcomes will be reassessed with local experts of the respective countries to assure feasibility before the start of the intervention.

Table 3: Hygiene-related health outcome variables for Module 4.

Outcome variable	Details
Absenteeism of health care worker	
 • Record of the event • Number of days absent • Reason for absence
Maternal mortality	
 • Record of the event • If known, reason of passing
Neonatal mortality	
 • Record of the event • If known, reason of passing
Neonatal sepsis(49)	
 • Record of the event • Number of days treated • Outcome (healthy, unknown, death)
Umbilical cord infection	
 • Record of the event • Number of days treated • Type of infection • Outcome (healthy, unknown, death)
Wound infection after stitching of surgical procedures	
 • Record of the event • Number of days treated • Outcome

Covariates were assessed with a directed acyclic graph (DAG) with RANAS variables as exposure variables and good handwashing practice as outcome variable (Appendix). Covariates for estimating the total effect of RANAS on good handwashing practice are age, education, sex, socio-economic status, previous training in hygiene, handwashing practices, position in the health care facility, and the water infrastructure of the health care facilities.

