Module 1: Combined RANAS and KAP survey	SO1: Hygiene-related RANAS behavioural factors of HCWs at baseline	- Descriptive statistics, multiple linear and logistic regression models
Module 2: Structured handwashing observations	SO1: Hygiene-related RANAS behavioural factors of HCWs at baseline SO2: Impact of h4h intervention on hygiene-related RANAS behavioural factors of HCWs	- Descriptive statistics, multiple linear regression models and logistic regression models
Module 3: Microbiological analysis of hand rinse samples	SO1: Hygiene-related RANAS behavioural factors of HCWs at baseline SO2: Impact of h4h intervention on hygiene-related RANAS behavioural factors of HCWs	- Analysis of E. coli and total coliforms - Descriptive statistics, multiple linear regression models
Module 4: Diary approach for pre-defined health outcomes	EO1: Effects of h4h intervention package on health outcomes and absenteeism	- Descriptive statistics
Module 5: Focus Group Discussions	SO3: Perceived effects of the h4h intervention package	- Framework methodology
Module 6: Key informant interviews	SO3: Perceived effects of the h4h intervention package	- Framework methodology

The Swiss TPH assessed the health care worker's understanding of hygiene and expected positive and negative impacts of the intervention with Gravit'eau with focus group discussions (FGDs) in 18 facilities in Mali and 9 facilities in Burkina Faso (more facilities are still being investigated). Local collaborators from Tdh and the regional ministries of health were involved from the study's kick-off meeting onwards and are regularly being consulted in bi-weekly meetings and additional ToC workshops led by Skat Foundation. The data collection methods for each module will be described in further detail:

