6.3.1.1 Primary Analysis

Module 1: Combined RANAS and KAP survey: The data will be summarized using descriptive statistics. Associations of RANAS behavioural factors with good handwashing practices and health care worker's characteristics with the other outcome variables from RANAS behavioural factors will be estimated using random effect linear regression modelling and random effect logistic regression modelling. Missing data will clearly be reported but not imputed.

Module 2: Structured handwashing observations: To quantify the intervention effect logistic regression with binomial distribution with random intercepts for health care facilities models will be applied.

Module 3: Microbiological analysis of hand rinse samples: For investigating factors associated to *E.coli* and total coliform prevalence on HCWs hands, random effect linear regression models will be applied.

Module 4: Diary approach for pre-defined health outcomes: . The sum of each outcome variable separately per facility will be used as a measure for statistical analysis. To quantify the intervention effect on hygiene-related health outcomes, random effect linear regression modelling will be used.

Modules 5 and 6, FGDs and KIIs: FGDs and KIIs will be audio recorded, transcribed, and translated if necessary for further analysis. The local perception of the success and sustainability of the h4h intervention will be analysed using the framework method with the software MaxQDA (VERBI Software, Marburg, Germany) or NVivo (QSR International, Melbourne, Australia) (48).

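### The covariate list for the effect of RANAS factors on good handwashing practice includes handwashing practices as its own item; read literally, the Module 1 regression would not estimate the stated total effect

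*Combined protocol and SAP*

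**What the plan says.** Section 4.2 describes a directed acyclic graph "with RANAS variables as exposure variables and good handwashing practice as outcome variable". It then gives the adjustment set: "Covariates for estimating the total effect of RANAS on good handwashing practice are age, education, sex, socio-economic status", followed by "previous training in hygiene, handwashing practices, position in the health care facility, and the water infrastructure of the health care facilities". The second item in that last run carries no qualifier such as baseline, past, observed or self-reported.

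The documents describe two measures of handwashing practice:

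- **Observed.** Section 4.1: "The primary endpoint is the number of times a participant performs good handwashing practice with soap at critical moments assessed by structured handwashing observations".
- **Self-reported.** Section 4.2, endpoint A: "Self reported handwashing practice to answer for each critical moment on a Likert scale ranging from almost never to almost always".

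Section 4 (Modules 1 and 2) schedules the survey and the observations at the same three rounds, linked by participant ID.

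The model concerned is in the Module 1 paragraph of section 6.3.1.1. It plans random-effect linear and logistic regressions for "Associations of RANAS behavioural factors with good handwashing practices" and names no covariates. Section 6.3.1.2 refers only in general terms to known confounders and predictors imbalanced at baseline. Section 4.2 is therefore the only explicit covariate list for this model.

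**The concern.** An adjustment set for a total effect should block confounding paths. It should not contain the outcome, or a variable that is a consequence or second measurement of the outcome. Here the outcome construct reappears among the covariates. An analyst who follows the list as punctuated must find a practice variable in the data. The ones described are the observation itself and the self-report taken in the same round as the RANAS items. Conditioning on either removes part or all of the association that the model is meant to quantify. Behavioural factors that matter could then look weak or irrelevant.

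**Working it through.** **No figure to reproduce.** The plan states no effect size, correlation or precision for this regression. The check has two parts: what the item could mean, and what adjustment would do under assumed values.

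**1. Possible meanings of the item**

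| Meaning of the item | Support in the documents | Effect on the model |
|---|---|---|
| The outcome measure, same round | Literal reading of section 4.2 | Degenerate: the RANAS coefficient goes to 0 |
| The other practice measure, same round | Literal reading; both measures described in sections 4.1 and 4.2 | Conditions on a proxy of the outcome; not a total effect |
| Training in handwashing | Follows directly on training in hygiene; section 4.3 mentions a survey question on last handwashing training | Not an adjustment for practice; this concern falls away |
| Practice at an earlier time | Possible for the later rounds, since section 4 repeats Modules 1 to 3 with linkable IDs; not stated | Can be a proper confounder |

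At baseline the last meaning has no described measure. There is no earlier round, and section 4.3 limits survey recall to one week apart from the training question.

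**2. Size if the covariate is a concurrent proxy**

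Assumptions: all variables are standardised; the RANAS-outcome correlation is ρ = 0.50; the proxy P equals the outcome Y plus noise; the noise is independent of RANAS; corr(Y, P) = r. Then corr(RANAS, P) = ρr, and the adjusted coefficient is

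(ρ − r·ρr) / (1 − ρ²r²) = 0.5(1 − r²) / (1 − 0.25r²).

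| r (assumed) | Numerator | Denominator | Adjusted effect | Loss from 0.50 |
|---|---|---|---|---|
| 0.2 | 0.480 | 0.9900 | 0.485 | 3% |
| 0.3 | 0.455 | 0.9775 | 0.465 | 7% |
| 0.5 | 0.375 | 0.9375 | 0.400 | 20% |
| 0.7 | 0.255 | 0.8775 | 0.291 | 42% |
| 0.9 | 0.095 | 0.7975 | 0.119 | 76% |

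**3. Cross-checks by simulation, also on assumed values**

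- Linear model with latent practice, 400,000 draws. With the proxy included, 84%, 67%, 47%, 25% and 0% of the unadjusted coefficient remains at proxy reliability 0.2, 0.4, 0.6, 0.8 and 1.0.
- Binomial model, five opportunities per worker, 2,000 workers, 100 replicates, no facility effect. The log odds ratio is 0.71 without the proxy, and 0.62, 0.49 and 0.25 with it at reliability 0.25, 0.5 and 0.8.
- Counter-case: the covariate is prior practice, a common cause of RANAS and outcome. The true log odds ratio is 0.80, unadjusted 1.10, adjusted 0.80. Adjustment is then correct.

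**4. If the proxy's error is not independent of RANAS**

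Self-report and RANAS items come from the same interview, and section 4.3 expects desirability bias. Write c for corr(RANAS, P); the general formula is (0.5 − rc)/(1 − c²). With r = 0.2, independence gives c = 0.10 and 0.485. If shared response bias raised c to 0.60 (assumed), the result is (0.5 − 0.12)/(1 − 0.36) = 0.38/0.64 = 0.59. So even the direction depends on the independence assumption.

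**The case against.** The strongest reply is that this is a drafting slip. The item sits right after training in hygiene, and the survey asks about last training on handwashing. The related lists in RQ 1.3 and section 6.1.2 name demographics, previous training and water infrastructure, but not practice. Those lists treat RANAS as the outcome, so they support the reading without settling it. The DAG, referred to an appendix that is not in the document text available, could settle it. This reply stands in part: it is not established that the authors mean to adjust for the outcome. But the list as printed says so, and nothing else in the text corrects it.

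A second reply is that the loss may be small. That also stands: at correlations of 0.2 to 0.3 it is 3% to 7%, and the documents give no correlation between self-report and observation.

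Three stronger readings are tempting and are not supported:

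- **That secondary objective 1 would be answered wrongly.** Table 2 in section 4 does place Module 1 under "SO1: Hygiene-related RANAS behavioural factors of HCWs at baseline". But the research questions for that objective concern the level of RANAS factors, the infrastructure, and predictors of RANAS factors. None estimates an effect of RANAS on handwashing.
- **That the behaviour-change package would be mis-steered.** Section 2.3.2 says statistical analyses identify the relevant factors, but no section says this covariate list is used for that step.
- **That the trial result is at risk.** Section 6.3 includes only the intervention as predictor in the primary analysis.

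**Conclusion.** The concern holds as a defect of the written covariate list. Followed literally, it puts the outcome or a concurrent proxy of it into the adjustment set for a total effect on that same outcome, and the model then does not estimate the effect named in section 4.2. That conclusion needs no numerical assumption.

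The size does. With independent error and a true standardised effect of 0.50, the loss runs from about 3% to 76% as the assumed correlation goes from 0.2 to 0.9, and is complete if the covariate is the outcome measure itself. With error shared between self-report and RANAS items, neither size nor direction is assured. If training or properly timed earlier practice was meant, the problem is one of wording only.

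The scope is the Module 1 RANAS-handwashing association analysis.

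**What to change.** Delete handwashing practices from the covariate list in section 4.2. If training was meant, write *previous training in hygiene and handwashing practices* as a single item. If earlier practice was meant, name the measure and its round, require that it precede the RANAS variables (for example baseline practice in models of the follow-up rounds), and show it as a separate node in the DAG. It would also help to state in the Module 1 paragraph of section 6.3.1.1 that this list is the one used, and whether the outcome there is observed or self-reported practice.

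The cost is one line of text and, at most, one node in the DAG. No data collection, sample size or primary analysis changes.
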